A Phase II Trial of Neoadjuvant PD 0332991, a Cyclin-Dependent Kinase (Cdk) 4/6 inhibitor, in Combination with Anastrozole in Women with Clinical Stage 2 or 3 Estrogen Receptor Positive and HER2 Negative Breast Cancer

Principal Investigator Signature Page

Principal Investigator:	[name]., Ph.D.	
<hr/> Signature of Investigator		<hr/> Date
<hr/> Printed Name of Investigator		

By my signature, I agree to personally supervise the conduct of this study and to ensure its conduct in compliance with the protocol, informed consent, IRB/HRPO procedures, the Declaration of Helsinki, ICH Good Clinical Practices guidelines, and the applicable parts of the United States Code of Federal Regulations or local regulations governing the conduct of clinical studies.
		

Contact Information

Principal Investigator: [name]., Ph.D.
Washington University School of Medicine
Division of Oncology
[name]
[name]
[contact]
[contact]
E-mail: [contact]

SCHEMA

PIK3CA Wild Type or Mutant Cohorts (Closed as of Amendment #7)

Eligible patients: clinical stage II or III ER+ HER2- breast cancer
with complete resection of tumor as a goal

[figure not shown]
Had Pre-registered to NCI 9170 trial* or this trial# and started the following procedure:

- #1: Tumor biopsy for PIK3CA mutation testing and research
- #2 Cycle 0 treatment¹: Anastrozole 1 mg PO daily Cycle 0 Days 1-28
If premenopausal add: Goserelin 3.6mg SC on Day 1

Endocrine Resistant Cohort

Clinical stage II or III ER+
HER2- breast cancer

Ki67 > 10% on neoadjuvant
endocrine therapy

¹Cycle 0 starts while waiting for the result of PIK3CA analysis

²Cycle length=28 Days

³Biopsy prior to PD0332991 is not required in the endocrine resistant cohort if the patient had a research tumor sample collected at the time of Ki67 analysis while on endocrine therapy

⁴Optional biopsy on Day 15 of subsequent cycles is recommended if C1D15 Ki67 was indeterminate or if not performed.

⁵Cycle 5 duration is 10-12 days and administered in patients whose absolute neutrophil is recovered to $\geq 1.5k/\text{mcL}$ and platelet $\geq 100k/\text{mcL}$ and treatment related AEs to grade 1 or less within 3 weeks after completion of cycle 4. Patients who do not meet this criteria may proceed to surgery in 3-5 weeks post cycle 4 day 21 PD0332991.

[figure not shown]

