to recover to \leq grade 1 as well as to accommodate surgery scheduling. Anastrozole is continued in all patients during the neoadjuvant period. Patients who receive goserelin should also continue goserelin every 28 days during the neoadjuvant period.

CBC+D is to be performed 3 days (± 1 day) prior to surgery in patients who receive Cycle 5 therapy. Treatment with PD 0332991 should be interrupted if ANC $<$ 1,000/mcL, platelets $<$ 100,000/mcL, or patients present with any \geq grade 2 treatment-related toxicities. If a patient needs to stop treatment prematurely in Cycle 5, she will have surgery on the scheduled date unless contraindicated, as the recovery of neutropenia is usually prompt after stopping PD 0332991 due to its mechanisms of action (investigator brochure). However, surgery may be rescheduled at the discretion of the treating physician and the study chair. Patients should continue with anastrozole until the day before surgery regardless of whether they complete Cycle 5 of PD 0332991.

Patients whose ANC and/or platelets do not recover within 3 weeks following the completion of Cycle 4 will proceed to surgery as planned (3 to 5 weeks following the last dose of PD 0332991 (Cycle 4 Day 21)). For these patients, anastrozole is to be continued until the day of surgery, with the last dose of anastrozole given the day before surgery.

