6.3 Re-Treatment Criteria for Neoadjuvant Cycles 1-4 and Adjuvant Therapy

A new cycle of treatment with PD 0332991 may begin only if:

- ANC \geq 1,000/mcL.
- Platelet count \geq 50,000/mcL.
- Non-hematologic toxicities have returned to baseline or Grade \leq 1 severity (or, at the Investigator's discretion, Grade \leq 2 if not considered a safety risk for the patient).

Criteria for dose interruption within cycle:

- ANC $<$ 1,000/mcL.
- Platelet count $<$ 50,000/mcL.

Re-treatment within the cycle may only be started when ANC \geq 1,000/mcL and platelet count \geq 50,000/mcL.

Doses omitted for toxicity within a cycle are not replaced or restored within the same cycle (meaning that the cycle remains 28 days regardless of the number of doses of taken).

If these conditions are not met, anastrozole treatment may be continued but treatment with PD 0332991 must be delayed by one week. If, after a one-week delay, all toxicities have recovered within the limits described above, treatment with PD 0332991 can be resumed.

If the patient has not recovered after 2 weeks (including the scheduled 1-week off treatment period within a cycle) despite dose reduction to the lowest dose level, treatment with PD 0332991 will be permanently discontinued.

Adjuvant PD 0332991 may be interrupted for a maximum of 4 weeks due to intercurrent illness or surgery (discuss with study chair).

Anastrozole is administered in a continuous regimen and therefore no re-treatment criteria apply.

6.4 Re-Treatment Criteria for Cycle 5

Cycle 5 Day 1 with PD 0332991 may begin only if:

- ANC \geq 1,500/mcL
- Platelet count \geq 100,000/mcL
- Non-hematologic toxicities have returned to baseline or Grade \leq 1 severity (or, at the Investigator's discretion, Grade \leq 2 if not considered a safety risk for the patient).

If these conditions are not met, anastrozole treatment will be continued but treatment with PD 0332991 will be delayed by one to three weeks. If all toxicities have recovered within the limits described above within 3 weeks, treatment with PD 0332991 for Cycle 5 will be initiated. If the patient has not recovered after a 3 week delay, treatment with PD 0332991 will be permanently discontinued and patients should proceed to surgery within 3 to 5 weeks after the last dose of PD0332991 (Cycle 4 Day 21) if possible.

Anastrozole is administered in a continuous regimen and therefore no re-treatment criteria apply.

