- K. Serum chemistry is albumin, alkaline phosphatase, total bilirubin, bicarbonate, BUN, calcium, chloride, creatinine, glucose, potassium, total protein, SGOT/AST, SGPT/ALT, sodium
- L. In premenopausal women only
- N. EKG will be performed at baseline, pre-surgery, and as needed. Surgery may be delayed if QTc prolongation has occurred.
- O. Mammogram and ultrasound of the diseased breast must be completed within 12 weeks prior to registration. Imaging studies must include bidimensional breast tumor measurements, but retrospective measurement is allowed in the study.
- P. C1D15 biopsy and blood draw may be done up to C1D20 for scheduling convenience, although C1D15 is strongly preferred.
- Q. Optional biopsy on C2D15, C3D15, or C4D15 in patients with indeterminate Ki67 on C1D15 biopsy or who missed the C1D15 biopsy.
- R. Research funded. Research blood samples are mandatory except where indicated.
- S. Optional
- T. If counts recover within 3 weeks of the end of C4, re-start PD 0332991 for 10 to 12 doses (C5) (last dose to be the day before surgery).
- U. PKs to be drawn on a day prior to initiation of PD 0332991 (may be C1D1) pre-anastrozole and again 90 minutes post-anastrozole. Other research blood include serum, plasma, whole blood for germline DNA and whole blood for circulating tumor DNA is also collected on C1D1. Details are described in Section 9.1.2. PK samples are not required in the endocrine resistant cohort.
- V. PKs to be drawn pre-dose of both drugs and again 90 minutes post-dose of both drugs. PK samples are not required in the endocrine resistant cohort.
- W. Not required in endocrine resistant cohort if a research biopsy was performed prior to registration or an archival tumor block is available
- Y. Only required in patients who are in Cycle 5.

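### Section 6.4 lets Cycle 5 start with grade 2 toxicity that schema footnote 5 bars and Section 5.1 says to interrupt for; and Section 15.5 pools surgical Ki67, arrest and PEPI 0 across women on and off PD 0332991

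*Combined protocol and SAP*

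**What the plan says.** Starting Cycle 5. Section 6.4 sets limits on ANC, platelets and non-hematologic toxicity. The last limit is baseline or grade 1, with discretion to accept up to grade "2 if not considered a safety risk for the patient". Once the limits are met: "If all toxicities have recovered within the limits described above within 3 weeks, treatment with PD 0332991 for Cycle 5 will be initiated". Schema footnote 5 has no such discretion; it asks for recovery of "treatment related AEs to grade 1 or less within 3 weeks after completion of cycle 4". Section 5.1 (Special Considerations for Cycle 5) lets Day 1 be delayed by up to 3 weeks so that other treatment-related events can settle to at most "grade 1 as well as to accommodate surgery scheduling". Calendar footnote T in Section 10.2 mentions only blood counts: "If counts recover within 3 weeks of the end of C4, re-start PD 0332991 for 10 to 12 doses".

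Stopping Cycle 5. Section 5.1 lists, among the triggers for interrupting PD 0332991, anything at or above the level of "grade 2 treatment-related toxicities". A woman who stops early normally keeps her surgery date, but "However, surgery may be rescheduled at the discretion of the treating physician and the study chair".

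Drug status at surgery. Women who complete Cycle 5 have surgery on its Day 11, 12 or 13 with the last dose the day before (Sections 5.1 and 5.2). Women who finish four cycles without Cycle 5 have surgery 3 to 5 weeks after Cycle 4 Day 21. Women with C1D15 Ki67 above 10%, or with confirmed progression, stop early and go to surgery or other treatment, which may be chemotherapy (Sections 5.7 and 9.3.1).

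Analysis. Section 15.5 separates analyses by cohort unless otherwise specified. It gives percent change in Ki67 from baseline, McNemar comparisons of arrest at C1D1, C1D15 and surgery, and the PEPI 0 rate with a 90% interval. It names no split by Cycle 5 receipt or time since the last dose.

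**The concern.** The first issue is a dosing rule that contradicts itself shortly before an operation. An investigator who follows Section 6.4 departs from the schema and starts a drug that Section 5.1 says to interrupt.

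The second is interpretability. Section 2.0 reports that Ki67 had risen at surgery in the first 18 patients, all operated on off drug. It reads this as a reversible drug effect but allows that resistant clones could explain it. Amendment #5 added Cycle 5 to investigate these explanations, yet Section 15.5 contains no analysis that separates on-drug from off-drug surgery.

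The same surgical values feed PEPI 0, which requires Ki67 of 2.7% or less and which Section 1.9.6 wants to set against a historical control. Through PEPI 0 they reach the OS and RFS comparisons. They also reach the Ki67 trajectory groups if surgery is a time point there, as that paragraph's heading suggests.

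**Working it through.** **1. The start rules, for a treatment-related non-hematologic grade 2 event still present after Cycle 4**

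| Text | What it implies |
|---|---|
| 6.4, start criteria | May start if judged not a safety risk |
| Schema footnote 5 | May not start |
| 5.1, delay sentence | Points to waiting for grade 1, but only permits a delay |
| 5.1, interruption rule | PD 0332991 should be interrupted |
| 5.1, route to surgery without Cycle 5 | Silent: names ANC and platelets only |
| 10.2, footnote T | Silent: names counts only |

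The firm conflicts are 6.4 against footnote 5, and 6.4 against the 5.1 interruption rule. The ANC and platelet start limits agree in 6.4, 5.1 and footnote 5. Events unrelated to treatment are outside the conflict, because footnote 5 and 5.1 restrict only treatment-related ones.

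**2. Days from last PD 0332991 dose to surgery**

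- Cycle 5 completed: 1 day.
- Stopped on the planned blood count, surgery date kept. The rule is "CBC+D is to be performed 3 days (± 1 day) prior to surgery in patients who receive Cycle 5 therapy", so the count falls 3 − 1 = 2 to 3 + 1 = 4 days before. With the last dose on that day or the day before, the gap is 2 to 5 days.
- Stopped after the Cycle 5 Day 1 dose, surgery date kept: 11 − 1 = 10 to 13 − 1 = 12 days. It is longer if surgery is moved; no maximum is stated.
- Four cycles, no Cycle 5: 3 × 7 = 21 to 5 × 7 = 35 days.
- Stopped early (C1D15 Ki67 above 10%, progression, other): not tied to Cycle 4 Day 21, and possibly after chemotherapy.

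**3. What pooling does to a rate**

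Simplify to two states. Let f be the off-drug share and d the on-drug minus off-drug arrest rate. Then pooled rate = on-drug rate − f × d.

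- f is at least 18/50 = 36% if the 18 are among the 50 women enrolled in the wild-type and mutant cohorts and all 50 contribute. It is at least 18/45 = 40% if the 18 are among the 45 with C1D15 Ki67 and only those contribute. Both are assumptions. Shares within each cohort are not given.
- d is not in the documents. Each 10 points of d moves the pooled rate by 0.36 × 10 = 3.6 to 0.40 × 10 = 4.0 points.

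For illustration, take on-drug arrest as 87% (the C1D15 result in Section 1.8, assumed to carry over to surgery), with the off-drug rate assumed:

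| Assumed off-drug rate | Pooled, 25% on drug | Pooled, 75% on drug |
|---|---|---|
| 30% | 44% | 73% |
| 44% | 55% | 76% |
| 60% | 67% | 80% |

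The drug's effect is the same across each row; only the Cycle 5 share differs.

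**4. What pooling does to McNemar**

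C1D15 is on drug for everyone. For women completing Cycle 5, C1D15 to surgery compares on drug with on drug, so lost arrest would suggest escape despite treatment. For women 3-5 weeks off drug it compares on with off, so lost arrest could be simple reversal. A pooled test counts both as the same discordant pair.

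**The case against.** On dosing, the exception is discretionary, and a site that always waits for grade 1 complies with 6.4, footnote 5 and 5.1 alike. The number of women affected is unknown, and two of the three neoadjuvant cohorts are closed. A reader might infer that Section 5.1 also forbids starting at grade 2. It does not: its start sentence permits a delay, and its route to surgery without Cycle 5 names counts alone. The interruption rule says should, and could be read as meant for toxicity that emerges during Cycle 5. All of this stands. It narrows the conflict but does not remove it, because footnote 5 is explicit and the interruption wording does not exempt toxicity already present.

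On analysis, the surgical results are secondary or exploratory, and Section 15.5 is silent rather than wrong: nothing bars a split later. Section 2.0 places the primary endpoint at C1D15 precisely because surgery was then off drug, and expects the surgical data only to help form hypotheses. That limits the weight of the point. Still, Amendment #5 gave the surgical sample a specific question, and leaving the split unstated leaves it to choice after the data are seen.

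A reader might also infer that every woman without Cycle 5 is 3-5 weeks off drug. Those stopped early are not, so a plain yes/no split on Cycle 5 would itself mix drug states.

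**Conclusion.** Both parts hold in this limited form and should be changed. The dosing conflict covers treatment-related non-hematologic grade 2 events and arises only when the 6.4 exception is used; its frequency is not given. The analysis gap covers surgical Ki67, arrest at surgery, PEPI 0 and what is built on them. Its effect on the reported rates cannot be sized, because no surgical arrest rates are given; the 36-40% off-drug share rests on the assumptions above and applies only to the combined wild-type and mutant cohorts.

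Two stronger conclusions are not supported. The primary endpoint is measured at C1D15, before Cycle 5, so it is untouched. And splitting by drug status would not prove reversibility: the groups are non-randomised, partly separated by calendar time, and selected on recovery from toxicity.

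**What to change.** **Dosing.** Delete the grade 2 exception in 6.4 for treatment-related events. Add non-hematologic recovery to the 5.1 sentence on proceeding to surgery without Cycle 5 and to footnote T. This serves the endocrine resistant cohort, the one still open for neoadjuvant enrollment.

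**Analysis.** In 15.5, report surgical Ki67, arrest at surgery and PEPI 0 descriptively by PD 0332991 status at surgery:

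1. Cycle 5 completed.
2. Cycle 5 interrupted, with days since last dose.
3. Four cycles completed without Cycle 5, flagging treatment before Amendment #5 or failed recovery.
4. Kept apart: stopped early for C1D15 Ki67 above 10%, progression or another reason, flagging any chemotherapy before surgery.

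Run the C1D15-to-surgery comparison within groups 1 and 3 only. Carry the status into the PEPI 0 outcome and trajectory analyses.

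**Cost.** Amendment wording and a table split from dosing and surgery dates already collected. The price is precision. At an observed 50%, the exact (Clopper-Pearson) 90% interval is 38-62% for 25/50 pooled, 34-66% for 16/32 and 29-71% for 9/18. Here 32 = 50 − 18, which assumes that all the other women form one group. Within one cohort it is worse: 15 evaluable mutant-cohort women over four equal groups (an assumption) is about 4 each, and 2/4 gives 10-90%. The split should therefore be labelled descriptive.

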7.0 REGULATORY AND REPORTING REQUIREMENTS

The entities providing oversight of safety and compliance with the protocol require reporting as outlined below.

The Washington University Human Research Protection Office (HRPO) requires that all events meeting the definition of unanticipated problem or serious noncompliance be reported as outlined in Section 7.2.

The FDA requires that all serious and unexpected adverse events be reported as outlined in Section 7.4. In addition, any fatal or life-threatening adverse experiences where there is a reasonable possibility of relationship to study intervention must be reported.

Pfizer requires that all events be reported as outlined in Section 7.7.

7.1 Definitions

7.1.1 Adverse Events (AEs)

Definition: any unfavorable medical occurrence in a human subject including any abnormal sign, symptom, or disease.

Grading: the descriptions and grading scales found in the revised NCI Common Terminology Criteria for Adverse Events (CTCAE) version 4.0 will be utilized for all toxicity reporting. A copy of the CTCAE version 4.0 can be downloaded from the CTEP website.

Attribution (relatedness), Expectedness, and Seriousness: the definitions for the terms listed that should be used are those provided by the Department of Health and Human Services' Office for Human Research Protections (OHRP). A copy of this guidance can be found on OHRP's website:

<http://www.hhs.gov/ohrp/policy/advevntguid.html>

7.1.2 Serious Adverse Event (SAE)

Definition: any adverse drug experience occurring at any dose that results in any of the following outcomes:

- Death
- A life-threatening adverse drug experience
- Inpatient hospitalization or prolongation of existing hospitalization
- A persistent or significant disability/incapacity (i.e., a substantial disruption of a person's ability to conduct normal life functions)
- A congenital anomaly/birth defect
- Any other experience which, based upon appropriate medical judgment, may jeopardize the subject and may require medical or surgical intervention to prevent one of the outcomes listed above

All unexpected SAEs must be reported to the FDA.

7.1.3 Unexpected Adverse Experience

Definition: any adverse drug experience, the specificity or severity of which is not consistent with the current investigator brochure (or risk information, if an IB is not required or available).

Events that are both serious AND unexpected must be reported to the FDA.

7.1.4 Life-Threatening Adverse Experience

Definition: any adverse drug experience that places the subject (in the view of the investigator) at immediate risk of death from the reaction as it occurred, i.e., it does not include a reaction that, had it occurred in a more severe form, might have caused death.

Life-threatening adverse experiences must be reported to the FDA.

7.1.5 Unanticipated Problems

Definition:

- unexpected (in terms of nature, severity, or frequency) given (a) the research procedures that are described in the protocol-related documents, such as the IRB-approved research protocol and informed consent document; and (b)

- the characteristics of the subject population being studied;
- related or possibly related to participation in the research (in this guidance document, possibly related means there is a reasonable possibility that the incident, experience, or outcome may have been caused by the procedures involved in the research); and
- suggests that the research places subjects or others at a greater risk of harm (including physical, psychological, economic, or social harm) than was previously known or recognized.

7.1.6 Noncompliance

Definition: failure to follow any applicable regulation or institutional policies that govern human subjects research or failure to follow the determinations of the IRB. Noncompliance may occur due to lack of knowledge or due to deliberate choice to ignore regulations, institutional policies, or determinations of the IRB.

7.1.7 Serious Noncompliance

Definition: noncompliance that materially increases risks, that results in substantial harm to subjects or others, or that materially compromises the rights or welfare of participants.

7.1.8 Protocol Exceptions

Definition: A planned deviation from the approved protocol that are under the research team's control. Exceptions apply only to a single participant or a singular situation.

Local IRB Pre-approval of all protocol exceptions must be obtained prior to the event. For secondary sites, the Washington University PI will issue approval of the exception, but it must also be submitted to the local IRB with documentation of approval forwarded to Washington University. HRPO approval is not required for protocol exceptions occurring at secondary sites.

7.2 Reporting to the Human Research Protection Office (HRPO) at Washington University

The PI is required to promptly notify the IRB of the following events:

- Any unanticipated problems involving risks to participants or others which occur at WU, any BJH or SLCH institution, or that impacts participants or the conduct of the study.
- Noncompliance with federal regulations or the requirements or determinations of the IRB.
- Receipt of new information that may impact the willingness of participants to participate or continue participation in the research study.

These events must be reported to the IRB within **10 working days** of the occurrence of the event or notification to the PI of the event. The death of a research participant that qualifies as a reportable event should be reported within **1 working day** of the occurrence of the event or notification to the PI of the event.

7.3 Reporting to the Quality Assurance and Safety Monitoring Committee (QASMC) at Washington University

The PI is required to notify the QASMC of any unanticipated problem occurring at WU or any BJH or SLCH institution that has been reported to and acknowledged by HRPO as reportable. (Unanticipated problems reported to HRPO and withdrawn during the review process need not be reported to QASMC.)

QASMC must be notified within **10 days** of receipt of IRB acknowledgment via email to a QASMC auditor.

7.4 Reporting Requirements for Secondary Sites

The research team at each secondary site is required to promptly notify the Washington University PI and research coordinator of all reportable events (as described in Section 7.6) within **1 working day** of the occurrence of the event or notification of the secondary site's PI of the event. This notification may take place via email if there is not yet enough information for a formal written report (using an FDA MedWatch form). A formal written report must be sent to the Washington University PI and research coordinator within **10 working days** of the occurrence of the event or notification of the secondary site's PI of the event. The death of a research participant that qualifies as a reportable event should be reported within **1 working day** of the occurrence of the event or notification of the secondary site's PI of the event.

The research team at a secondary site is responsible for following its site's guidelines for reporting applicable events to its site's IRB according to its own institutional guidelines. The research team at Washington University is responsible for reporting all applicable events to the FDA.

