7.6 Reporting to the FDA

The conduct of the study will comply with all FDA safety reporting requirements. **PLEASE NOTE THAT REPORTING REQUIREMENTS FOR THE FDA DIFFER**

FROM REPORTING REQUIREMENTS FOR HRPO/QASMC. It is the responsibility of the Washington University principal investigator to report any unanticipated problem to the FDA as follows:

- Report any unexpected fatal or life-threatening adverse experiences (Section 7.1.4) associated with use of the drug by telephone or fax no later than **7 calendar days** after initial receipt of the information.
- Report any serious, unexpected adverse experiences (Section 7.1.2), as well as results from animal studies that suggest significant clinical risk within **15 calendar days** after initial receipt of this information.

All MedWatch forms will be sent by the investigator or investigator's team to the FDA at the following address or by fax:

Food and Drug Administration
Center for Drug Evaluation and Research
Division of Oncology Drug Products
[name]
[name]
FAX: [name]

Secondary sites must submit a completed MedWatch form to the Washington University PI and research coordinator within **4 calendar days** (for fatal or life-threatening adverse experiences) or **11 calendar days** (for serious, unexpected adverse experiences). The Washington University PI will be responsible for submitting all MedWatch forms from secondary sites to the FDA within the timeframes specified above.

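### Sections 7.4 and 7.6 give secondary sites conflicting deadlines for the same MedWatch form: 10 working days against 4 or 11 calendar days

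*Combined protocol and SAP*

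**What the plan says.** Section 7.4 (Reporting Requirements for Secondary Sites) sets out three steps.

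- **Notice.** Sites must notify the coordinating center "of all reportable events (as described in Section 7.6) within 1 working day of the occurrence of the event", or of the site PI learning of it. Email is acceptable at this point: "This notification may take place via email if there is not yet enough information for a formal written report (using an FDA MedWatch form".
- **Written report.** "A formal written report must be sent to the Washington University PI and research coordinator within" 10 working days, counted from the event or from the site PI's notification. The preceding sentence identifies this report as the MedWatch form.
- **Deaths.** "The death of a research participant that qualifies as a reportable event should be reported within 1 working day of the occurrence of the event". No form is named in this rule.

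Section 7.6 (Reporting to the FDA) also addresses the sites: "Secondary sites must submit a completed MedWatch form to the Washington University PI and research coordinator within" 4 calendar days if the event is fatal or life-threatening, or 11 calendar days if it is serious and unexpected. The coordinating PI reports unexpected fatal or life-threatening events to the FDA by telephone or fax within 7 calendar days of first receiving the information. Serious, unexpected events go to the FDA within 15 calendar days. The PI must also forward the secondary sites' MedWatch forms to the FDA within those same periods.

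Section 7.0 directs readers to Section 7.4 for FDA reporting, although the FDA rules are in 7.6.

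**The concern.** The two sections cannot be separated by scope. Section 7.4 defines its reportable events by reference to 7.6, and the sender, the recipients and the form are the same in both. Only the deadline differs, and no order of precedence is given.

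A secondary site can therefore follow the section headed for it exactly and still breach another section of the same protocol. The larger gap falls on the more urgent events, where 7.6 allows 4 calendar days. The wrong pointer in Section 7.0 makes it easier to land on the longer deadline. At stake are the timely arrival of the completed form at the coordinating center, its onward submission to the FDA as 7.6 requires, and an avoidable audit finding.

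**Working it through.** There is no sample size, power or error rate to reproduce here. The check is a conversion of working days to calendar days.

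**Inputs**
- Section 7.4: notice in 1 working day, form in 10 working days.
- Section 7.6, site to PI: form in 4 or 11 calendar days.
- Section 7.6, PI to FDA: 7 or 15 calendar days.

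**Conventions.** The day the site becomes aware is day 0, weekends are excluded, and there are no holidays. *N* is the calendar day of the 1-working-day notice if sent on the last permitted day. *F* is the calendar day on which the 10-working-day form falls due. Section 7.6 gives no starting point for its 4 and 11 days; I assume the same start as 7.4.

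**Formulas**
- Overrun of the 7.6 site deadlines: *F* − 4 and *F* − 11.
- Days past the 7-day FDA period: *F* − 7 from awareness; *F* − (*N* + 7) from the notice.
- Days left before the 15-day limit: 15 − *F* from awareness; (*N* + 15) − *F* from the notice.

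| Day 0 | N | F | F−4 | F−11 | F−7 | F−(N+7) | 15−F | (N+15)−F |
|---|---|---|---|---|---|---|---|---|
| Mon–Thu | 1 | 14 | 10 | 3 | 7 | 6 | 1 | 2 |
| Fri | 3 | 14 | 10 | 3 | 7 | 4 | 1 | 4 |
| Sat | 2 | 13 | 9 | 2 | 6 | 4 | 2 | 4 |
| Sun | 1 | 12 | 8 | 1 | 5 | 4 | 3 | 4 |

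**Results**
- The 7.4 deadline is 12 to 14 calendar days. It is 8 to 10 days later than the 4-day deadline and 1 to 3 days later than the 11-day deadline.
- For a life-threatening event, the form falls 5 to 7 days after the 7-day period counted from awareness, and 4 to 6 days after it counted from the notice.
- The 15-day limit is still met, with 1 to 3 days left from awareness or 2 to 4 from the notice.

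**Sensitivity.** One weekday holiday in the second week moves *F* to between 15 and 17, which removes the slack against 15 days counted from awareness. If day 0 is itself counted as working day 1, the earliest deadline is day 11 (a Monday event: that Friday is working day 5, the next Friday working day 10, which is 11 days later). That would just meet the 11-day limit but is still past days 4 and 7.

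**Comparison.** Under the 7.6 deadlines the form arrives 7 − 4 = 3 days before the 7-day limit, or 15 − 11 = 4 days before the 15-day limit, from awareness. This spacing suggests that the 4- and 11-day limits were set to feed the two FDA limits.

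**The case against.** The strongest case on the other side is that the practical harm is small, and much of it stands.

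- A reader might infer that a site following 7.4 makes the PI miss the 7-day FDA report. The documents do not support that. The report is made by telephone or fax, runs from the PI's first receipt, and can rest on the notice that 7.4 requires within 1 working day. It does not need the completed form.
- A reader might also infer that safety signals reach investigators late. The coordinating PI hears within 1 working day. Section 7.5 gives the PI 10 working days, from the event or the PI's notification, to inform the other sites; that clock does not wait for the form.
- Reportable deaths have their own 1-working-day rule in 7.4, so the 7-day problem falls mainly on non-fatal life-threatening events.
- It cannot be assumed that sites will follow 7.4. That section itself refers to 7.6, which addresses the sites directly, and a site meeting 4 or 11 days would also satisfy 10 working days.
- Section 7.7 requires serious events to reach the drug supplier within 24 hours using a MedWatch form, which makes a 10-working-day wait less likely in practice. It does not settle the conflict, because it leaves the secondary sites' own time frame undefined.

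None of this removes the contradiction. The early notice protects the first FDA report, but not the requirement in 7.6 that the sites' completed forms arrive, and are forwarded, within the stated periods.

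**Conclusion.** The inconsistency is real and affects both event classes. Compliance with 7.4 permits a breach of 7.6 by 8 to 10 calendar days for fatal or life-threatening events and by 1 to 3 days for other serious, unexpected events. For an unexpected, non-fatal, life-threatening event, the form can reach the PI too late to be forwarded to the FDA within 7 days, whether the period runs from site awareness or from the notice. For the 15-day limit the consequence is thin slack, normally not a breach.

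The figures assume no holidays, day 0 not counted as a working day, and a common starting point for the two sections' clocks. The 7- and 15-day limits are taken from Section 7.6 itself.

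This is an operational error in a safety-reporting rule. It does not affect the endpoint, sample size, error rates or analysis, and it is a minor correction.

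**What to change.** In Section 7.4, replace the 10 working days for the MedWatch form with the 4- and 11-calendar-day limits already in 7.6, or with a direct reference to them. Keep the 1-working-day notice and the 1-working-day rule for deaths. In Section 7.0, change the pointer for FDA reporting from 7.4 to 7.6.

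The cost is about one sentence and one cross-reference. No new limit is introduced: sites are already bound by the 7.6 deadlines.
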